4.4.2. Discontinuation of Investigational Product

Subjects must discontinue investigational product for any of the following reasons:

- Sponsor request, for reasons such as significant protocol deviation (and after discussion with the investigator).
- Study is terminated by the Sponsor.
- Subject meets PML discontinuation criteria (see [Appendix 4](#)).
- Subject develops any other serious opportunistic or atypical infection.
- Subject meets liver chemistry stopping criteria (see [Appendix 3](#)).
- Subject initiates treatment with a prohibited PV disease-modifying drug.
- Subject becomes pregnant.
- Subject experiences a serious or life-threatening cardiac arrhythmia.

Any subject who discontinues from the Treatment Period should complete an Early Withdrawal Visit and transition into the Individualized Follow-up Period for important safety monitoring (as applicable; see Section 3.1.3), unless he/she meets a criterion for mandatory withdrawal from the study (see Section 4.4.3).

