** This amendment was superseded by Protocol Amendment 5 before implementation at any study center **

Section	Original Text	Changes	Rationale
Section 3	NA	Added: ** Refer to Appendix 2 (or protocol addendum) for any applicable country-specific requirements. **	Regulatory authorities from the UK and France requested protocol change(s) that have been added to Appendix 2,
Section 4	NA	Added: ** Refer to Appendix 2 (or protocol addendum) for any applicable country-specific requirements for subject inclusion in this study. **	Country-Specific Requirements ; therefore, cross-references to this appendix have been added within the protocol.
Appendix 2 – France and Appendix 2 – UK	Change regarding Section 4.2, Inclusion criterion 7b. ... use of acceptable methods of contraception... informed consent and lasting until 6 months after last dose,,,	... use of acceptable methods of contraception... informed consent and lasting until 12 months after last dose,,,	Request by France and UK national competent authorities for alignment with ARZERRA (ofatumumab for IV infusion) EU SPC.
Appendix 2 – UK	Change regarding Section 4.2, Inclusion criterion 7b. ... Complete abstinence from heterosexual intercourse	Complete abstinence from heterosexual intercourse, when this is in line with the preferred and usual lifestyle of the subject	Request by UK national competent authority.

Protocol Amendment 5: 02 April 2015

Applicable to all countries and study centers, unless otherwise specified as a country-specific requirement. At the time of this amendment, 5 subjects had been randomized in the study.

[figure not shown]
Section	Original Text	Changes	Rationale
Title page	NA	Protocol amendment number, date, and revision chronology.	Amendment 5.
Throughout	NA	Corrections and clarifications for consistency throughout protocol, Cross-references to country-specific criteria, as applicable.	To address inconsistencies and questions identified while initiating study centers and subject enrollment.
Definitions	NA	Added definitions for study periods	Added study period definitions to list of clinical definitions for ease of locating.
Summary; Section 1.2	...mortality rate of 40% ...mortality to approximately 5% to 15% [Robinson, 1997; Langan, 2008].	...mortality rate of 40% ...mortality from 70% to less than 20% [Carson, 1996; Langan, 2008].	Updated with publication of a retrospective analysis of mortality rates.

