Protocol Amendment 7: 25 April 2016

Applicable to all countries and study centers.

At the time of this amendment, 35 subjects had been randomized in the study.

** OPV116910 Amendment 6 was not implemented at any study center. As a result, conduct of the study for all study centers transitioned from Amendment 5 directly to Amendment 7 (ie, nonconsecutive numbering) **

Section	Original Text	Changes	Rationale
Title page	NA	Protocol amendment number, date, and revision chronology.	Amendment 7
Protocol-specific definitions; Protocol summary, Study design; Section 3.1	If B-cell counts have not recovered by the Week 60 visit, subjects not entering the extension study will remain in an Individualized Follow-up Period until either the CD19+ B-cell counts or circulating IgG levels are \geq LLN or baseline levels (if $<$ LLN) or until 2 years after the last dose of investigational product (whichever comes first).	If B-cell counts have not recovered by the Week 60 visit, subjects not entering the extension study will remain in an Individualized Follow-up Period until both the CD19+ B-cell counts and circulating IgG levels are \geq LLN or baseline levels (if $<$ LLN) or until 2 years after the last dose of investigational product (whichever comes first).	Based on discussion with investigators, criteria for maintaining subjects in the Individualized Follow-up Period were modified to allow for improved safety monitoring following last dose of investigational product, while facilitating the exit of subjects from the study in order to progress to alternative treatment if needed.
Section 3.1, Figure 3-2	Meet any of these criteria: 
 • CD19+ B-cells or IgG \geqLLN or baseline? • Meet other criteria for study withdrawal/exit? • 2 years after the last dose? AND HBV monitoring complete (if applicable)?	Meet any of these criteria: 
 • CD19+ B-cells and IgG \geqLLN or baseline? • Meet other criteria for study withdrawal/exit? • 2 years after the last dose? AND HBV monitoring complete (if applicable)?	

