4.2. Final Analysis

The study was terminated early and the final analysis will be conducted on the available data.

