9.1.2.2. Remission

For the secondary endpoint of the proportion of subjects in remission on minimal steroid therapy at Week 60, subjects who discontinued treatment prior to Week 60 will be considered as not in remission at Week 60.

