11.1. Primary Efficacy Analyses

11.1.1. Time to SR on Minimal Steroid Therapy by Week 60

The co-primary efficacy endpoint of time to SR on minimal steroid therapy by Week 60 (as defined in Section [2.2.1](#)) will be analyzed using a log-rank test stratified by baseline prednisone/prednisolone dose and disease duration strata. Subjects who discontinue prematurely (prior to Week 60) and who have not achieved remission upon discontinuation will be censored at the time they discontinued. Subjects who reach Week 60 without remission will be censored at the date of their last visit.

For subjects achieving remission, time to SR on minimal steroid therapy will be derived as: [(the date on which the subject initially tapered his/her oral prednisone/prednisolone dose to ≤ 10 mg/day and maintained ≤ 10 mg/day of oral prednisone/prednisolone with no new or nonhealing (established) lesions for ≥ 8 weeks and maintained that status until Week 60) – (the date of randomization)] + 1 day.

A summary table presenting the Kaplan-Meier estimates for the time to SR and 95% CI at Week 4, week 8, Week 12 etc. for each of the treatment groups and p-value for the treatment difference, using the 2-sided log-rank test indicated above will be presented for the ITT population and PP population (if criteria are met as discussed in Section [11](#)).

For the covariate analysis, a summary table computing hazard ratio and 95% CI for the hazard ratio and the p-value using the Cox proportional hazards model discussed in Section [8.2](#), will be presented for the full model for the ITT population.

A Kaplan-Meier plot of time to SR on minimal steroid therapy will be constructed for each treatment group for the ITT population.

11.1.2. Duration of Remission on Minimal Steroid Therapy by Week 60

The co-primary endpoint of duration of remission on minimal steroid therapy will be analyzed using a rank ANCOVA [[Stokes 2000](#)], with treatment as a main effect, and baseline prednisone/prednisolone dose and disease duration strata as covariates. If a subject discontinues the study prior to Week 60, the subject will be considered as not in remission from the date of the last known study visit until Week 60.

For subjects who complete the study without experiencing any periods of remission, duration of remission on minimal steroid therapy will be 0 days.

One Period of Remission

For subjects who experience one period of remission on minimal steroid therapy that:

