- Is continuing at the Week 60 study visit (or early discontinuation):

- Duration of remission on minimal steroid therapy will be derived as: [(the date of the Week 60 study visit/date of last known visit) - (the date on which an absence of new or nonhealing lesions occurs while the subject is on a prednisone/prednisolone dose of ≤ 10 mg/day for ≥ 8 weeks)] + 1 day.
- Relapses/flare prior to the Week 60 study visit (or early discontinuation):
 - Duration of remission on minimal steroid therapy will be derived as: [(the date on which flare/relapse occurs) - (the date on which an absence of new or nonhealing lesions is found while the subject is on a prednisone/prednisolone dose of ≤ 10 mg/day for ≥ 8 weeks)].

Note that for periods of remission that end with relapse/flare, “+ 1 day” is not included in the calculation since the end date is the date on which relapse/flare occurs so the subject is not considered to be in remission on that day.

More Than One Period of Remission

For subjects who experience more than one period of remission on minimal steroid therapy (i.e. a subject went into remission, then relapsed, and then went into remission again (or possibly more than 2 episodes of remission)) the duration of remission will be the sum of all periods of remission while on minimal steroid therapy up to Week 60.

Individual periods of remission will be defined as specified above for subjects experiencing one period of remission. Duration of remission will be derived as the sum of all individual periods of remission.

A summary table computing the raw duration and p-value for the treatment difference, using the rank ANCOVA indicated above, will be presented for the ITT population and PP population (if criteria are met as discussed in Section [11](#)).

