11.2. Secondary Efficacy Analyses

11.2.1. Proportion of Subjects Achieving Remission on Minimal Steroid Therapy at Week 60

A subject’s daily dose of prednisone/prednisolone will be obtained from the steroid taper log that is completed at all in-clinic and telephone study visits between Weeks 2 and 60.

The absence of new or nonhealing lesions will be determined from the lesion evaluation performed at all post-baseline in-clinic study visits.

The proportion of subjects achieving remission on minimal steroid therapy at Week 60 will be analyzed using a Cochran-Mantel-Haenszel (CMH) test stratified by baseline prednisone/prednisolone dose and disease duration. In this analysis, subjects who discontinued prior to Week 60 will be considered as not having remission at Week 60.

A summary table presenting the proportion of subjects achieving remission on minimal steroid therapy and the proportion of subjects not achieving remission on minimal steroid therapy for each of the treatment groups and the p-value for the treatment difference, using the CMH test indicated above, will be presented for the ITT population.

11.2.2. Time to Remission While on Minimal Steroid Therapy by Week 60

A subject's daily dose of prednisone/prednisolone will be obtained from the steroid taper log and the determination of the absence of new or nonhealing lesions will be obtained from the lesion evaluations performed at all post-baseline in-clinic study visits.

Time to remission on minimal steroid therapy, as defined in Section 9.2.5, will be analyzed using a log-rank test stratified by baseline prednisone/prednisolone dose and disease duration. Subjects who discontinue prematurely (prior to Week 60) will be censored at the time they discontinued. Subjects who reach Week 60 without remission will be censored at their last visit.

A summary table presenting the Kaplan-Meier estimates for time to remission on minimal steroid therapy and 95% CI at Week 4, week 8, Week 12 etc. for each of the treatment groups and p-value for the treatment difference, using the 2-sided log-rank test described above, will be presented for the ITT population.

A Kaplan-Meier plot of time to remission on minimal steroid therapy will be constructed for each treatment group.

11.2.3. Time to Initial Flare/Relapse by Week 60

[figure not shown]

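### The Week-60 remission rules treat subjects stopped by the sponsor's termination like any other dropout, which dilutes the treatment difference

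*SAP*

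**What the plan says.** SAP 4.2 states: "The study was terminated early and the final analysis will be conducted on the available data". SAP 1 keeps the core analyses as first planned, and SAP 1, 4.1 and 8.3 drop the interim analysis and the multiplicity procedure. The Week-60 scoring is not adapted:

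- **Duration of remission (SAP 11.1.2).** After a stop before Week 60, "the subject will be considered as not in remission from the date of the last known study visit until Week 60". A remission still continuing at that point ends at "the date of the Week 60 study visit/date of last known visit", so days up to the last visit are kept.
- **Week-60 proportion.** SAP 9.1.2.2: "subjects who discontinued treatment prior to Week 60 will be considered as not in remission at Week 60". SAP 11.2.1: "subjects who discontinued prior to Week 60 will be considered as not having remission at Week 60".
- **Time to sustained remission (SR).** SAP 9.1.2.1 censors everyone who discontinues before Week 60. SAP 11.1.1 censors only those who had not achieved remission when they discontinued.

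None of these rules refers to the reason for stopping. Protocol 4.4.2 lists "Study is terminated by the Sponsor" among the reasons for which study drug must be stopped.

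**The concern.** Scoring a leaver as not in remission is defensible when leaving reflects how the subject was doing. A stop imposed by the sponsor on a calendar date carries no such information. As written, a subject in remission on a low steroid dose on that date is a Week-60 failure, just like one who left because of flares. Whether a subject can be a responder then depends partly on how early he or she was randomised.

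SAP 8.3 still reports two-sided 5% p-values for these endpoints. A small, non-significant Week-60 difference could be read as lack of efficacy when much of it is truncated follow-up.

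**Working it through.** **1. The design figures reproduce.** Protocol 8.2.1 gives 54% and 80% SR, a hazard ratio of 0.48248, 80 events, 13% dropout and N = 136.

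- Hazard ratio: ln(0.46)/ln(0.20) = 0.48248.
- Schoenfeld events for 90% power at two-sided 0.05: 80.
- N: 118/(1 − 0.13) = 136. Also 80/(0.67 × 0.87) = 137.2, within 3%.

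**2. How many could have reached Week 60.** Randomised counts in Protocol Appendix 15:

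| Amendment | Date | Randomised |
|---|---|---|
| 5 | 2 April 2015 | 5 ("At the time of this amendment, 5 subjects had been randomized in the study") |
| 6 | 28 September 2015 | 21 |
| 7 | 25 April 2016 | 35 ("At the time of this amendment, 35 subjects had been randomized in the study") |
| 8 | 5 September 2016 | 35 |

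The text for Amendment 7 says the study had already been terminated, but no termination date is given. The last two amendment dates are used here as assumed stops. Sixty weeks is 420 days.

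- Stop on 25 April 2016: Week 60 requires randomisation by 2 March 2015. Five subjects were in by 2 April 2015, so at most 5.
- Stop on 5 September 2016: randomisation by 13 July 2015, which falls between Amendments 5 and 6, so between 5 and 21.

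**3. Dilution of the Week-60 proportion.** Let f be the share able to reach Week 60. With everyone else scored as a failure, the expected rates are 0.54f and 0.80f, and the difference is 26f points. At f = 0.40 this is 21.6% against 32.0%, or 10.4 points. At f = 0.12 it is 3.1 points.

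Power at N = 69 (34.5 per arm) uses the normal approximation for two proportions with pooled variance under the null. At f = 0.40, with pooled rate 0.268:

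- null SE = √(2 × 0.268 × 0.732/34.5) = 0.107
- alternative SE = √((0.216 × 0.784 + 0.320 × 0.680)/34.5) = 0.106
- power = Φ((0.104 − 1.96 × 0.107)/0.106) ≈ 16%

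| f | SAP rule | Only subjects whose 60 weeks could elapse |
|---|---|---|
| 1.0 | 64% | 64% |
| 0.6 | 26% | 42% |
| 0.4 | 16% | 30% |
| 0.2 | 9% | 17% |

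The restricted analysis brings the expected rates back to 54% and 80% at any f. With N = 35 and f = 0.4, power is 10% under the SAP rule and 17% restricted.

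**4. Simulation of both endpoints.** 4,000 trials per setting, N = 69, 1:1, exponential time to remission giving 54% and 80% by Week 60, no flares, a common calendar stop, and accrual shaped on the amendment counts.

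| | No early stop | Stop 5 Sep 2016 (f = 0.40) | Stop 25 Apr 2016 (f = 0.12) |
|---|---|---|---|
| Power, proportion | 65% | 16% | 7% |
| Power, duration | 65% | 55% | 40% |
| Rejection with no effect, proportion | 5.3% | 5.4% | 4.0% |
| Rejection with no effect, duration | 5.0% | 5.0% | 5.2% |

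Under the two early stops, follow-up length explains 13.5% and 22.9% of the variance in the duration ranks, and treatment arm 7.5% and 5.6%. Adding flares gave the same pattern.

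**5. Why duration depends on entry date.** Under the taper table (Protocol Table 3-2), starting at Week 2 and without flare, a 120 mg starter reaches 10 mg at Week 24 and completes eight weeks at Week 32. For 60 mg the weeks are 18 and 26; for 20 mg they are 8 and 16. A 120 mg starter stopped at Week 30 has zero days in either arm.

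**The case against.** The strongest reply is that the comparison remains valid. Allocation is 1:1 and concurrent, so entry date is balanced between arms in expectation. A reader might infer that the endpoints now measure randomisation date rather than drug effect, or that the arms are biased against each other. The documents do not support that: simulated rejection with no effect is 4.0% to 5.4%, and the expected difference keeps its sign.

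Duration is hurt less than the proportion, because accrued days up to the last visit count. The Week 30 example covers only a high starting dose.

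A reader might also infer that a subject in remission at termination can never be an SR event. The endpoint does require status held to Week 60, but SAP 9.1.2.1 and 11.1.1 differ on such a subject, and those clearly covered are censored, not failed. The plan leaves this case unsettled.

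The size is uncertain. Protocol 3.1 as amended after termination still speaks of subjects completing the study, so f could be well above the low scenarios. Shares computed on 35 subjects, such as 5/35 = 14%, cannot be taken as established when SAP 5 reports 69.

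Finally, p-values are nominal, withdrawal reasons are tabulated by arm (SAP 10.1), and time to remission, which does not need Week 60, is already planned with censoring (SAP 11.2.2).

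All of this limits the claim. None of it supplies a rule that separates a sponsor stop from a failure.

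**Conclusion.** The concern holds as one of dilution. Followed as written, the SAP counts administratively stopped subjects as Week-60 failures and truncates their remission time. The Week-60 difference shrinks to about 26f points, power falls, and the absolute rates in each arm have no clear meaning. Direction and type I error are preserved. The proportion suffers most, duration moderately.

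The power figures rest on the protocol's 54% and 80%, an assumed common stop date and accrual following the amendment counts. The simulation applies that accrual shape to 69 subjects. If the total is 69 but only 5 to 21 could have reached Week 60, f would be 5/69 = 7% to 21/69 = 30%. The limits of 5 and 21 themselves depend on the amendment counts being correct. The counts of 35 and 69 must therefore be reconciled before any value of f is quoted.

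**What to change.** 1. Reconcile the number randomised (35 in Amendments 7 and 8, 69 in the SAP) and state the termination date.
2. In SAP 9.1.2, 11.1.2 and 11.2.1, flag stops due to sponsor termination, using the withdrawal reason already recorded, and report them by arm. Keep the not-in-remission rule for all other stops.
3. Add a Week-60 proportion analysis limited to subjects randomised at least 60 weeks before the termination date. The set depends on randomisation date only, so the comparison stays randomised.
4. For duration, add potential follow-up (randomisation to the earlier of Week 60 and termination) as a covariate in the rank ANCOVA. Dividing days by follow-up is not enough, because the taper weeks cannot count. Counting from Week 32, a 120 mg starter could reach at most 28/60 = 47% with 60 weeks but 8/40 = 20% with 40 weeks.
5. State one time-to-SR rule for subjects in remission at termination, replacing the differing wording in SAP 9.1.2.1 and 11.1.1.
6. Present the planned time to remission on minimal steroid therapy alongside, without demoting the co-primary endpoint.
7. Keep the present scoring as a reported analysis. Label the additions as specified after termination and after the sponsor's unblinding (Protocol Appendix 15, Amendment 7).

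The cost is SAP wording, one flag and a few tables. The drawbacks are a small denominator for the restricted proportion, possibly too small for a stratified test, and analyses added late.

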11.1.3. Consistency Criterion for Co-Primary Endpoint Significance

The protocol planned to check the consistency criterion for the analysis of co-primary endpoints to protect the overall type-I error at 0.05 (one-sided 0.025) using the procedure by Alosch and Huque [Alosch 2010]. But now since the study is terminated, the efficacy endpoints tables will only be presented with the p-value at a two-sided 0.05 level of significance without any further adjustments for multiplicity.

11.2. Secondary Efficacy Analyses

11.2.1. Proportion of Subjects Achieving Remission on Minimal Steroid Therapy at Week 60

A subject’s daily dose of prednisone/prednisolone will be obtained from the steroid taper log that is completed at all in-clinic and telephone study visits between Weeks 2 and 60.

The absence of new or nonhealing lesions will be determined from the lesion evaluation performed at all post-baseline in-clinic study visits.

The proportion of subjects achieving remission on minimal steroid therapy at Week 60 will be analyzed using a Cochran-Mantel-Haenszel (CMH) test stratified by baseline prednisone/prednisolone dose and disease duration. In this analysis, subjects who discontinued prior to Week 60 will be considered as not having remission at Week 60.

A summary table presenting the proportion of subjects achieving remission on minimal steroid therapy and the proportion of subjects not achieving remission on minimal steroid therapy for each of the treatment groups and the p-value for the treatment difference, using the CMH test indicated above, will be presented for the ITT population.

11.2.2. Time to Remission While on Minimal Steroid Therapy by Week 60

A subject's daily dose of prednisone/prednisolone will be obtained from the steroid taper log and the determination of the absence of new or nonhealing lesions will be obtained from the lesion evaluations performed at all post-baseline in-clinic study visits.

Time to remission on minimal steroid therapy, as defined in Section 9.2.5, will be analyzed using a log-rank test stratified by baseline prednisone/prednisolone dose and disease duration. Subjects who discontinue prematurely (prior to Week 60) will be censored at the time they discontinued. Subjects who reach Week 60 without remission will be censored at their last visit.

A summary table presenting the Kaplan-Meier estimates for time to remission on minimal steroid therapy and 95% CI at Week 4, week 8, Week 12 etc. for each of the treatment groups and p-value for the treatment difference, using the 2-sided log-rank test described above, will be presented for the ITT population.

A Kaplan-Meier plot of time to remission on minimal steroid therapy will be constructed for each treatment group.

11.2.3. Time to Initial Flare/Relapse by Week 60

[figure not shown]
Lesion evaluation will be performed at all in-clinic study visits, including whether the subject is currently experiencing flare/relapse and, in the event that the subject has self-reported a flare/relapse since the last scheduled visit, the date of the first onset of flare was reported by the subject is collected.

[figure not shown]
Time to initial flare/relapse, as defined in Section 9.2.6, will be analyzed using a log-rank test stratified by baseline prednisone/prednisolone dose and disease duration. Subjects who discontinue prematurely (prior to Week 60) will be censored at the time they discontinued. Subjects who reach Week 60 without flare/relapse will be censored at their last visit.

A summary table presenting the Kaplan-Meier estimates for time to initial flare/relapse and 95% CI at Week 4, week 8, Week 12 etc for each of the treatment groups and p-value for the treatment difference, using the log-rank test described above, will be presented for the ITT population.

For the covariate analysis, a summary table computing hazard ratio and 95% CI for the hazard ratio and the p-value using the Cox proportional hazards model discussed in Section [8.2](#), will be presented for the full model for the ITT population.

A Kaplan-Meier plot of time to initial flare/relapse will be constructed for each treatment group.

